
401 6. Generalized Anxiety Disorder-7 (GAD-7). The GAD-7 (Spitzer, Kroenke, Williams, & Lowe, 2006) will be used to assess generalized anxiety symptomology. This is a 7-item measure that asks participants to rate the frequency with 402 403 which they have been bothered by anxiety symptoms within the past two weeks on a scale ranging from 0 ("not at all") to 404 3 ("nearly every day"). Scores on all items are summed to obtain a total severity score. Scores reflect no significant 405 anxiety symptoms (0-4), mild anxiety symptoms (5-9), moderate anxiety symptoms (10-14), and severe anxiety symptoms 406 (>15). Respondents also indicate the degree to which their anxious symptoms have made it difficult for them to do their 407 work, take care of things at home, or get along with other people, from "not difficult at all" to "extremely difficult." The GAD-7 has been shown to have high internal consistency (e.g., α = .89; Lowe et al., 2008) and has been shown to reliably 408

- discriminate between anxious and non-anxious diagnostic groups (Kroenke, Spitzer, Williams, & Lowe, 2010).
- 7. Patient Health Questionnaire 9 (PHQ-9). The PHQ-9 is a widely used and well-validated instrument for measuring
 the severity of depressive symptoms (Kroenke, Spitzer, & Williams, 2001). It consists of 9 items that assess both affective

and somatic symptoms related to depression and depressive disorders; these 9 items correspond to the diagnostic criteria 412 for DSM MDD. Respondents rate the frequency with which they have been bothered by depressive symptoms within the 413 past two weeks (for baseline and follow up visits) or the past week (for interim assessment visits)on a scale ranging from 414 0 ("not at all") to 3 ("nearly every day"). Scores on all items are summed to obtain a total severity score. Scores reflect no 415 significant depressive symptoms (0-4), mild depressive symptoms (5-9), moderate depressive symptoms (10-14), 416

417 moderately severe depressive symptoms (15-19), and severe depressive symptoms (>19). Respondents also indicate the 418 degree to which their depressive symptoms have made it difficult for them to do their work, take care of things at home, or 419 get along with other people, from "not difficult at all" to "extremely difficult." The PHQ-9 has high internal consistency (e.g., alpha ranging from .83 to .92; Cameron, Crawford, Lawton, & Reid, 2008), and correlates strongly with other measures of 420 depression (Kroenke et al., 2001). 421

8. Tinnitus Acceptance Questionnaire (TAQ). The Tinnitus Acceptance Questionnaire (TAQ) was reported by Westin et 422 al. (2008). This measure captures the extent to which individuals accept their tinnitus, and attempts to avoid or control 423 tinnitus, as well as a patient's ability to pursue valued life activities and meaningful goals regardless of tinnitus. The TAQ 424 was further validated in an English speaking population (Weise et al., 2012). 425 426

Table 1 Measures and Assessments	Time (Min)	Aim
Screening Assessments and Main Outcomes		
1. [^] Demographics and Military Service Characteristics Form	5	I/E
2. *History of Head Injuries	5	I/E
3. ^MRI Screening Questionnaire	5	I/E
4. ^Life Events Checklist (LEC)	5	I/E
5. *Clinician-Administered PTSD Scale – 5 (CAPS-5)	50	1,2,3
6. ^PTSD Checklist (PCL-5)	5	1,2,
7. ^Tinnitus Functional Index (TFI)	5	1,2,
8. *rs-fMRI Scan & Tinnitus Data Collection Page	60-75	2,3
9. ^Hyperacusis Questionnaire (HAQ)	5	I/E
10. *~Audiometric Assessment	60	I/E
-Tinnitus & Hearing Healthcare History Questionnaire, tympanometry, pure tone air-		
and bone-conduction, speech testing, loudness discomfort, quick speech in noise test,		
tinnitus evaluation, & DPOAE		
11. ~Repeat Tinnitus Assessment when available	30	-
Group Characterization Measures		
1. [^] Health Questionnaire (HQ)	10	-
2. ^Alcohol Use Disorders Identification Test (AUDIT)	5	-
3. ^Deployment Risk and Resilience Inventory (DRRI-2) Combat Experience	5	-
4. ^Deployment Risk and Resilience Inventory (DRRI-2) Postbattle Experiences	5	-
5. [^] Trauma Related Guilt Inventory (TRGI)	5	-
6. ^Generalized Anxiety Disorder-7 (GAD)	5	-
7. ^Patient Health Questionnaire – 9 (PHQ-9)	5	-
8. [^] Tinnitus Acceptance Questionnaire (TAQ)	5	-
	280 -	-
Total Time (Min) over three visits	295	

6.3.2 Data Collection. 465

427

467 6.3.2.1 Instrumentation:

468 See the table at Section 6.2 above for a summary and description of the assessments and timing of administration. A

description of each of the assessments can be found in the previous section of this protocol. Assessments will be

administered in person whenever possible. However, we may collect assessments in person, via phone, video conferencing,
 and/or electronic data capture using a secure link to the encrypted STRONG STAR database.

4/1 and/or electronic data capture using a secure link to the encrypted STRONG ST 472

473 **6.3.2.2. Resting state** *f***MRI.**

Participants who are eligible to continue in the study after consent and screening will undergo a resting-state function
magnetic resonance imaging (rs- fMRI) session at the Research Imaging Institute (RII) at the University of Texas Health
Science Center at San Antonio. Participants who cannot tolerate the MRI procedure will be withdrawn from the study. Each
MRI scan may take up to 75 minutes. Participants will be asked whether they hear their tinnitus before the MRI scan, whether

they heard the tinnitus during the scan, and whether their tinnitus changed since the last time asked. Data will be recorded on the Tinnitus Data Collection Page.

480

492

504

481 **6.3.2.3 Data Storage and Access:**

Data will be coded using an assigned number. Paper research data will be kept in locked file cabinets in locked offices at the University of Texas Health Science Center San Antonio (UTHSCSA) STRONG STAR offices; the Research Imaging Institute (RII), or the Hearing Center of Excellence at Wilford Hall Ambulatory Service Center at Lackland Air Force Base (HCE). Data collected will be entered into a spreadsheet located on a secure STRONG STAR server. Audio-recordings of assessments will be uploaded to a secure STRONG STAR server over an encrypted network connection.

Neuroimaging data will be kept on secure networks at the Research Imaging Institute. Audiometric data will be kept under
 lock and key at the HCE. Every member of the Research Team will be trained and monitored about how to handle and
 protect both medical and research records. Furthermore, the Research Team strictly controls access to study data using
 policies and procedures developed specifically for the STRONG STAR Research Consortium.

493 6.4 Statistical Consideration494

495 **6.4.1 Primary (i.e., primary outcome variables) and secondary endpoints.**

496
 497 Primary outcomes include results based on measures of PTSD (CAPS-5 and PCL-5) and tinnitus-related distress (TFI and
 498 TAQ). The additional primary outcome is changes in functional activity within resting-state networks, provided by fMRI scans.
 499

500 Secondary outcome variables include measures of depression and suicide (PHQ-9), anxiety (GAD-7), and alcohol use 501 (AUDIT). 502

503 **6.4.2 Hypotheses, Sample Size Estimation, and Specific Data Analysis Plans.**

505 Hypothesis 1: Canonical correlations will identify both shared and unique symptoms between tinnitus-related distress and 506 PTSD.

507 Analysis Plan: Non-inferential statistics will be calculated to include central tendencies, standard deviations, and alpha coefficients. Prior to analyzing data, unusual distributions, missing data, or outliers will be identified. Descriptive 508 509 statistics will be used to summarize participant characteristics. Group differences will be tested using t-tests, Chi-Square, or Fisher's exact tests as needed. Canonical correlations will be conducted on the data of all 60 participants from the T&P 510 and TO groups, using the subscale scores of the CAPS-5 and the TFI. Canonical correlations identify and measure 511 512 associations among two sets of variables and will identify latent variables between tinnitus-related distress and PTSD 513 symptoms. The 12 total subscales from the CAPS-5 and TFI will be entered into the analyses, requiring 60 participants for 514 large effect sizes (Steven, 1986).

515

516 Hypothesis 2a: Dysregulated connectivity within the auditory-vigilance resting state network will be implicated among

517 individuals with both tinnitus and PTSD.

- 518 Hypothesis 2b: Individuals with tinnitus and PTSD will demonstrate unique patterns of dysregulation within the auditory-
- 519 vigilance network, versus those with only PTSD, only tinnitus, and healthy controls.

Analysis plan: rs-fMRI provides valuable information about neurobiological mechanisms that influence 520 neurological and psychiatric conditions at rest (Menon, 2011). To test our conceptual model and deduce neurobiological 521 mechanisms, we will use an existing, well-documented, 20-component parcellation scheme of the resting-state networks 522 (Laird et al., 2011; Auditory Component 16). After extracting the A1/VAN, we will use group information-guided 523 524 independent components analysis (GIG-ICA) to determine intra-network connectivity differences between those with both 525 tinnitus and PTSD, only PTSD, only tinnitus, and healthy controls. Our team (Vanasse et al., 2019) found robust 526 differences between active-duty service members with PTSD, combat controls, and civilian control (50 active-duty with 527 PTSD, 28 combat-exposed controls, and 25 civilian controls). Based on those results, 120 participants (30 per group) in 528 this proposed study, a priori power analyses demonstrated power of 80% when $\alpha = 0.05$, to detect an effect size of d = 529 0.31 (ANOVA: Fixed effects, omnibus one-way; Faul et al., 2007). Secondary analyses will examine functional connectivity between A1/VAN and other resting-state networks. 530 531

532 Hypothesis 3: Dysregulated activity within regions of the auditory-vigilance network will be correlated with symptom 533 clusters of both tinnitus-related distress and PTSD.

534 Analysis plan: Correlations will be conducted between functional connectivity within the auditory-vigilance resting state 535 network with tinnitus-related distress and PTSD symptoms. Power analyses predict that 57 participants will achieve a 536 power of .95, with an effect size d = .45, and alpha = .05 (R Core Team, 2014).

538 Missing data. If missing data can be assumed to be missing at random, likelihood-based mixed model analysis will 539 provide valid inferences using data from all cases with any outcome data. The impact of attrition on analyses will be addressed by comparing those who are available for analysis at each assessment with those who are not using 541 appropriate data from prior assessments. 542

543 6.5 Confidentiality

537

544

554

557

563

564

568

569

570

All in-person interview assessments will be delivered in private offices at the STRONG STAR Clinic or RII at the 545 546 UTHSCSA, or the HCE. This study involves remote and/or virtual research interactions with participants by the research staff. Research activities will be audio-recorded by an independent device (separate from the conferencing platform, i.e. 547 548 Zoom). Therefore, privacy and confidentiality is not guaranteed due to the nature of the electronic conferencing platforms that will be used. Data will be stored by an assigned participant code number. Digital audio recordings of assessments 549 will be labeled with the participant's study id number and uploaded onto the secure STRONG STAR server. Encrypted 550 email will be used to securely send recordings to research experts who are part of the research team for review of fidelity. 551 552 Every member of the Research Team will be trained and monitored about how to handle and protect both medical and 553 research records. Furthermore, the Research Team strictly controls access to study data.

555 6.5.1 Certificate of Confidentiality.

556 We are not seeking a Certificate of Confidentiality.

6.5.2. Data Protection. Data will be coded using an assigned number. Assessments will be stored in a locked cabinet at
 the STRONG STAR Clinic at the UTHSCSA, the RII, or HCE. Digital audio recordings of assessments will be labeled with
 the participant's study id number and uploaded onto the secure STRONG STAR server.

562 7.0 RISKS/BENEFITS ASSESSMENT

7.1 Risks.

565 566 **Risks and Side Effects related to the Assessment of Tinnitus**

567 Rare, but not Serious, expected to occur in less than 5 out of 100 participants:

• Emotional distress due to tinnitus or more attention toward tinnitus sensation may occur; however, since tinnitus is a chronic and stable condition, it is unlikely that a change will occur because of the assessment procedures

571 **Risks and Side Effects related to the Assessment of PTSD**

572 Likely, but not Serious, expected to occur in less than 5 out of 100 participants:

574

575

578

579 580

581

582 583 Title: An Evaluation of Neurobiological Similarities of Tinnitus and Posttraumatic Stress Disorder

• The assessment of PTSD and trauma-related events may produce some discomfort or emotional distress and can even produce a temporary increase in PTSD symptoms.

576 **Risks and Side Effects related to the Resting-State fMRI**

577 Rare, but not Serious, expected to occur in less than 5 out of 100 participants:

- Confinement claustrophobia (fear of tight spaces). During the MRI scan, participants will be asked to remain
 perfectly still. The MRI can cause individuals to feel claustrophobic (fear of tight spaces). However, the incidence
 of claustrophobia with the MRI is low (approximately 1 per 150 persons).
 - Hyperacusis. Individuals with hyperacusis who are sensitive to noise may experience some distress related to. the loudness of the fMRI procedure.

584 Rare and Serious, expected to occur in less than 5 out of 100 participants:

- Identification of incidental, asymptomatic lesions of unknown significance
- 586 Occasionally, previously unsuspected lesions that are not causing any symptoms may be found as a result of the 587 research scan. In these instances, a member of the Research Team (Principal Investigator: [name]) will contact 588 the participant, explain the abnormality that was found and give copies of the scans to the participant. The 589 participant will be encouraged to visit with their primary care provider to see if any action should be taken. A 590 follow-up letter that describes the incidental findings will be mailed to the participant.
- Foreign bodies which may interact with the magnetic field of the MRI can have risk for persons with foreign bodies implanted in their body. Cardiac pacemakers and cochlear implants may cease to function and can be permanently damaged by the MRI. Surgical clips on aneurysms and intestines may be moved by the magnetic field. Ferrous metal filings in the eye (e.g., in machinists) can be moved by the magnetic field. Foreign body risk is minimized by including only volunteers with no known foreign bodies and no exposure to circumstances, which might predispose to foreign bodies (e.g., metal machine workers). Before any MRI, we will ask participants about any metal objects that may be in their body in order to ensure their safety.
- 599 Safeguards for Protecting Participants: One of the risks with assessment of mental health conditions is identification of suicidality or harm of others. Participants will be provided immediate coping tools and techniques used to manage 600 distressing emotions by a licensed therapist. Distress experienced by participants is expected to be temporary. Any 601 indication that the participant is considering suicide will be handled using processes developed by military and civilian 602 Consultants for the STRONG STAR Consortium studies. Trained clinicians and evaluators will assess history of suicide 603 and current suicidal ideation using the following standardized measures: Patient Health Questionnaire-9 (PHQ-9). For 604 605 participants identified as having low to moderate risk for suicide based on the assessment results, the patient will be allowed to remain in the study but will be referred to the research audiologist or primary care provider as applicable for 606 607 appropriate follow up within standard of care. For participants identified as being at high risk for suicide based on the assessment results, they will be excluded from the study and will be referred for more intensive treatment (outpatient or 608 609 inpatient). 610
- 611 The diagnostic assessment testing may also indicate PTSD symptoms, anxiety, depression, or alcohol use that warrants treatment, Additionally, unsuspected lesions or hearing changes may be found as a result of the research testing. In these 612 instances, a member of the Research Team will contact the participant, explain the test findings and, if appropriate, 613 encourage the participant to see their primary care provider. The research testing is not being done to diagnose health 614 615 problems, and so the participant will need to see their primary care provider to see if any action should be taken. The research team can help facilitate communication with the primary care provider and provide local resources. For active 616 duty personnel, the military command will NOT be notified, and the results of the research testing will NOT be placed in 617 618 the medical record.
- 619
- A STRONG STAR Data Safety and Monitoring Plan (DSMP) has been developed in accordance with the National
 Institutes of Health (NIH) Office of Human Research Protection (OHRP) to assure the appropriate clinical safety and
 adverse event monitoring of study subjects participating in STRONG STAR studies.
- 623

624 7.2 Potential Benefits.

The knowledge gained from this study will serve to inform the most effective early interventions for the treatment of co-morbid tinnitus and PTSD in Veterans and service members. Results may provide a compelling argument that an underlying neurobiological mechanism contributes to comorbid tinnitus and combat-related PTSD, suggesting a different phenotype for
 this comorbidity. A different phenotype may explain non-responsiveness to trauma-focused therapy, causing a significant
 public health concern. Finding neurobiological markers of both disorders will prompt novel behavioral and neuro-modulatory
 therapies to target and regulate specific brain networks.

632 **7.3 Alternatives:**633

631

634

635

636 637

638

639

640

641

642

643

644

645

646

647 648

649 650 Treatments for PTSD that are available include the following:

- Various forms of psychotherapy (talk therapy) including CPT for PTSD.
- Various forms of psychotherapy (talk therapy) including Acceptance and Commitment Therapy for tinnitus
- Drug treatments for PTSD
- There may be other research studies involving experimental treatments that could be helpful in treating PTSD and/or tinnitus

Treatments for tinnitus are available include the following:

- Acceptance and Commitment Therapy
- Progressive Tinnitus Management
- Tinnitus Retraining Therapy
- Cognitive Behavioral Therapy for Tinnitus

Not participating in this study is an option.

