Overlapping Symptoms and Comorbidity. The same traumatic event could cause PTSD and tinnitus (e.g., IEDs). Tinnitus 61 62 can be conceptualized as a conditioned stimulus, reminding the individual of the traumatic event (Criterion B of PTSD; APA, 2013), as in flashbacks (Hinton et al., 2006). Those with tinnitus also show symptoms of avoidance (Criterion C of 63 PTSD). Veterans with both tinnitus and PTSD, and those with only tinnitus, reported similar aversions to loud signals and 64 65 lower tolerance to loud noises (Fagelson, 2007), which may result in decreased social interaction and engagement in pleasurable activities (Jastreboff & Jastreboff, 2002). Negative alterations in mood and cognition (Criterion D of PTSD) are 66 67 observed in those with tinnitus, and tinnitus-associated trauma and catastrophic cognitions predict PTSD severity (Hinton et al., 2006). Finally, individuals with tinnitus show emotional reactions that overlap with vigilance or hyperarousal 68 69 (Criterion E of PTSD), including startle responses, anger, and irritability (Fagelson & Smith, 2016), and sleep disturbance (McKenna, 2000). The high comorbidity between tinnitus and PTSD also suggests a common etiology that leads to 70 impairment and distress. Our recent study ([name] et al., 2020a) found a latent factor between tinnitus-related distress 71 72 and PTSD symptoms among veterans with PTSD, tinnitus, and posttraumatic headache. Based on this evidence, we posit 73 that PTSD exacerbates impairment among individuals with tinnitus. More research is needed to investigate psychiatric contributions to tinnitus-related distress, such as PTSD, with a possible unique phenotype when tinnitus and PTSD co-74 occur.

75 oc 76

Functional Outcomes. Functional outcomes for those with both tinnitus and PTSD are significantly worse than those with
 tinnitus only, or tinnitus and any other psychological disorder (Fagelson & Smith, 2016). This suggests a particularly
 deleterious combination of symptoms that exacerbate, and possibly maintain each disorder. It is feasible to treat
 psychiatric distress, and if successful, tinnitus-related distress will also decrease. Civilians with tinnitus had less tinnitus related distress after receiving trauma-focused therapy (Rikkert et al., 2018), but they were not evaluated for PTSD.
 These studies demonstrate the association between tinnitus and PTSD. More research is warranted to elucidate the

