6.2. Study Procedures and Description of Assessments

A trained research staff member will explain the study to potential participants in a private location and give them a copy of the informed consent document to read. The staff member will review the risks and benefits of the study and ensure the potential subject understands the research. Once consent is given, the screening assessments will then be scheduled. Timing of assessments will be determined by participants' availability. Group assignment, main outcomes, and participant characterization measures are described below. **Table 1** lists assessments.

259 Group Assignment

Participants will be assigned to one of four groups, based on results of audiometric assessments and the Clinician 260 Administered PTSD Scale for DSM-5 (CAPS-5), explained below. Those who indicate they have bothersome tinnitus and 261 262 meet criteria for PTSD on the CAPS-5 (conducted by an independent evaluator), will be assigned the Tinnitus and PTSD Group (T&P). Those who do not endorse tinnitus and meet criteria for PTSD will be assigned to the PTSD Only Group 263 264 (PO). Those who indicate they have bothersome tinnitus but do not meet criteria for PTSD will be assigned to the Tinnitus Only Group (TO). Those who do not endorse tinnitus and do not meet PTSD criteria on the CAPS-5 will be assigned to 265 266 the Healthy Control Group (HC). All will then be scheduled for an fMRI scan. Participants will be matched across groups for sex, age, head injury, length of military service, number of deployments, and hearing loss. Measures used for group 267 268 assignment and characterization are explained below.

270 Assessment Instruments.

The audiometric assessments will be conducted at the Hearing Center of Excellence (60 minutes). Repeat tinnitus acoustic assessment only (see description below) may be completed at the RII prior to the fMRI for eligible participants with tinnitus when an evaluator is available (30 minutes).

Self-report instruments may be administered at the Hearing Center of Excellence, at the STRONG STAR offices, or via
 online data capture, Clinical interviews may be administered at the STRONG STAR offices or via phone or video
 conferencing. These assessments are estimated to take approximately 90 minutes.

278

282

284

269

274

258

fMRI scans will be conducted at the Research Imaging Institute (60-75 minutes). Participants will be asked whether they

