305	apply). Each nominal point will be scored separately, as either 0 (=not endorsed by participant) or 1 (=endorsed by
306	participant).
307	5. The Clinician-Administered PTSD Scale for DSM-5 (CAPS-5; Weathers, et al., 2013) is a semi-structured interview,
308	conducted by an independent evaluator, that measures DSM-5 symptoms of PTSD. Presence of at least one intrusion
309	symptom, one avoidance symptom, two cognition and mood symptoms, and two arousal symptoms for 1 month or more
310	are required to reach the diagnostic threshold. Selection of Index Event for CAPS-5 will be used as a supplement to the
311	CAPS-5 interview to help determine which event to select as the Index Event. This form is standardly used in conjunction
312	with the CAPS-5 and does not represent a separate assessment. The CAPS-5 will be used to determine whether
313	participants meet criteria for PTSD for group determination and is a central variable in the study.
314	6. PTSD Check List – DSM-5 (PCL-5). The PCL-5 (Weathers, et al., 2010) is a 20-item self-report measure update of the
315	PCL designed to assess PSTSD symptoms as defined by the DSM-5. The PCL-5 is currently available and has been
316	shown to have good psychometric properties. The PCL-5 evaluates how much participants have been bothered by PTSD
317	symptoms in the past month (for baseline and follow up assessments) as a result of a specific life event. Each item of the
318	PCL-5 is scored on a five point scale ranging from 0 ("not at all") to 4 ("extremely).
319	7. The Tinnitus Functional Index (TFI; Meikle et al., 2011) has documented validity for scaling the severity and negative
320	impairment of tinnitus for use in intake assessment, and for responsiveness to treatment. The TFI will be used to
320	
	determine group assignment and to control for tinnitus-related distress in analyses.
322	8. Resting-State Functional Magnetic Resonance Imaging (rs-fMRI). We will acquire BOLD fMRI images in an
323	unstimulated state using an extended time-series (300 whole-brain volumes over ~ 60-75 min). These data are a main
324	outcome. Data will be processed on an ongoing basis to ensure integrity, and includes controlling for white matter,
325	cerebral spinal fluid, and movement.
326	9. Hyperacusis Questionnaire (HAQ). The Hyperacusis Questionnaire (HAQ; Khalfa et al., 2002) is a self-report
327	questionnaire that evaluates various hyperacusis symptoms. The HAQ consists of three factors, including attentional,

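### The Hypothesis 1 canonical correlation pools two groups split on the CAPS-5 with no group term, so on its own it cannot separate a PTSD-status difference from symptom-level overlap

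*Combined protocol and SAP*

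**What the plan says.** Section 6.2 (Group Assignment) builds both groups from people with bothersome tinnitus and separates them on the CAPS-5. For the comorbid group, those who also "meet criteria for PTSD on the CAPS-5 (conducted by an independent evaluator), will be assigned the Tinnitus and PTSD Group (T&P"). For the other: "Those who indicate they have bothersome tinnitus but do not meet criteria for PTSD will be assigned to the Tinnitus Only Group" (TO). The CAPS-5 description in section 6.2 sets the diagnostic threshold across all four symptom clusters: at least one intrusion "symptom, one avoidance symptom, two cognition and mood symptoms, and two arousal symptoms for 1 month or more".

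Section 6.4.2 (Hypothesis 1, Analysis Plan) then puts the two groups together: "Canonical correlations will be conducted on the data of all 60 participants from the T&P" "and TO groups, using the subscale scores of the CAPS-5 and the TFI". On size it says: "The 12 total subscales from the CAPS-5 and TFI will be entered into the analyses, requiring 60 participants for" large effects. The output is to be read as latent variables linking tinnitus-related distress with PTSD symptoms, and the hypothesis is that it will show which symptoms are shared and which are unique.

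No group term, within-group run, partial canonical correlation or sensitivity analysis is described. Tests of group differences are planned, and groups are to be matched on sex, age, head injury, length of service, deployments and hearing loss. Symptom severity is not a matching variable.

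On whether TFI means should differ, section 4 (Functional Outcomes) reports: "Functional outcomes for those with both tinnitus and PTSD are significantly worse than those with" tinnitus alone. The same section posits that PTSD worsens impairment in people with tinnitus. It gives no size.

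**The concern.** The measure that forms one of the two variable sets also decides who is in which group, and the 30:30 mix is fixed by design. CAPS-5 means must therefore differ between T&P and TO. If TFI means differ as well, the two mean gaps alone produce a non-zero pooled canonical correlation, even if CAPS-5 severity and TFI severity are unrelated within each group. The first pair of variates can then largely restate PTSD status, with loadings that follow whichever subscales differ most between groups.

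Hypothesis 1 is about particular symptoms. A finding that people with PTSD report more tinnitus distress is a different and weaker statement than a finding that specific PTSD and tinnitus symptoms vary together. The pooled result alone does not tell the reader which one was found. The planned group tests can reveal a mean gap but do not take it out of the canonical correlation, and the matching does not address it.

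**Working it through.** **The plan's own figure.** 30 + 30 = 60, and 12 subscales × 5 per variable = 60. Both are exact, but the ratio of five is inferred. Hypothesis 1 has no stated alpha, power or target canonical correlation, so 60 cannot be reproduced as a power calculation.

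**Inputs from the documents.** n = 30 per group; 12 subscales in total; four CAPS-5 clusters; hence 12 − 4 = 8 TFI subscales (by subtraction, not stated).

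**Assumptions.** The documents give no CAPS-5 gap, TFI gap or correlation between subscales. Gaps below are in within-group SDs and apply equally to every subscale of a set. The test is the global Wilks test at 0.05; the plan names no test or alpha for Hypothesis 1.

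**Step 1: closed form.** With zero cross-correlation inside each group and a 50:50 mix, the pooled first canonical correlation is

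r = √[A/(1+A)] × √[B/(1+B)], where A = Dx²/4 and B = Dy²/4.

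Dx² and Dy² are the squared Mahalanobis distances between groups on the CAPS-5 and TFI sets. For an equal gap d on k subscales with common correlation c, D² = k·d²/[1+(k−1)c].

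Example with c = 0.5, CAPS-5 gap 2 SD, TFI gap 0.8 SD:
- Dx² = 4×4/2.5 = 6.4, so A = 1.6 and A/(1+A) = 0.615.
- Dy² = 8×0.64/4.5 = 1.138, so B = 0.284 and B/(1+B) = 0.221.
- r = √(0.615×0.221) = 0.37, although no symptom is associated with any other across the two sets within either group.

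**Step 2: how often a test would reject with no within-group association.** 4,000 simulated datasets per row, c = 0.5, CAPS-5 gap 2 SD, Bartlett chi-square:

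| TFI gap (SD) | Population r | Pooled rejection | Group-centred rejection |
|---|---|---|---|
| 0 | 0.00 | 5.6% | 5.2% |
| 0.3 | 0.15 | 6.7% | 5.1% |
| 0.5 | 0.25 | 10.8% | 5.3% |
| 0.8 | 0.37 | 24.8% | 5.5% |
| 1.2 | 0.49 | 50.7% | 5.2% |

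A second simulation (within-set correlation 0.6, CAPS-5 gap 2 to 3 SD, Rao's F) gave pooled rejection of 10-12% at 0.5 SD, 21-28% at 0.8 SD and 30-43% at 1.0 SD. A repeat of that set-up agreed, with 20-25% at 0.8 SD. Over CAPS-5 gaps of 1.5 to 3 SD and c of 0.5 or 0.7, the range is 7.8-13.2% at 0.5 SD and 12.8-32.9% at 0.8 SD. At 0.3 SD it is 6.6-8.4%.

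**Step 3: what adjustment costs.** Now let the relation be real and continuous, with the groups formed by a median cut on CAPS-5 severity:

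| Latent correlation | Pooled rejection | Group-centred rejection |
|---|---|---|
| 0.5 | 36% | 14% |
| 0.6 | 60% | 22% |
| 0.7 | 84% | 34% |

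A similar simulation with latent correlations of 0.4 to 0.8 produced CAPS-5 gaps of 1.6-2.0 SD and TFI gaps of 0.4-1.2 SD. These overlap the gaps assumed in step 2, so the mean gaps alone do not reveal which situation holds.

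**The case against.** The strongest reply is that PTSD group is a coarse version of the CAPS-5 itself, not an outside confounder. If PTSD severity and tinnitus distress are related across people with tinnitus, a TFI gap between T&P and TO is what one would expect to see. The rejections in step 2 are errors only if TFI distress steps up at the diagnostic line and is flat on either side. Section 4 reports a latent factor between tinnitus distress and PTSD symptoms in an earlier sample, which points towards a continuous relation. This stands. A reader might infer that a pooled association would be spurious, or that the pooled analysis is invalid. The documents do not support that: for the broad question of whether the two symptom sets are related among people with tinnitus, the pooled analysis is legitimate.

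It also stands that every SD gap is assumed. The evidence in section 4 concerns functional outcomes, not the TFI. The same section reports similar sound aversion in the two groups, and both must have bothersome tinnitus, which may narrow the gap. With no TFI gap there is no inflation.

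A third reply is that Aim 1 is exploratory and states no test, so a Type I error rate presumes a decision rule the plan lacks. That is fair, but it does not remove the issue, because the loadings carry the group difference with or without a p-value. Nor can the raw coefficient be read instead: with 4 and 8 variables and n = 60, the sample first canonical correlation averages about 0.51 when there is no association at all.

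**Conclusion.** The point holds as a limit on interpretation. The plan pools two groups defined by one of its own variable sets, without a group term, and the pooled result alone cannot tell a PTSD-status difference from covariation among specific symptoms. With no within-group association and a CAPS-5 gap of 2 to 3 SD, a 0.05 Wilks test would reject in about 10%, 20-28% and 30-43% of runs at TFI gaps of 0.5, 0.8 and 1.0 SD, and barely above nominal at 0.3 SD or less. These figures rest on assumed gaps, within-set correlations and test.

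A reader might go further and require a symptom to load within groups before it is called shared. That does not follow. Because group is a cut on the CAPS-5, adjustment removes genuine CAPS-5 variation, and in step 3 it costs more than half the power. Simulations without any CAPS-5 split make adjustment look almost free (50.8% pooled against 50.3% adjusted at a within-group canonical correlation of 0.5), but that is not this design.

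**What to change.** In section 6.4.2, Hypothesis 1:

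- Keep the pooled canonical correlation and label it as including the PTSD-group difference.
- Pre-specify beside it a group-adjusted canonical correlation on the same 60 participants (both sets centred within group, or partial canonical correlation on group, with one degree of freedom removed).
- State how the two will be read together. If an association appears only in the pooled run, report that it may reflect PTSD status rather than specific shared symptoms.
- State that the adjusted run has low power, is not the sole criterion for calling a symptom shared, and that a null result in it is not evidence against overlap.
- Name the test and alpha for Hypothesis 1.

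The cost is a few sentences and one extra run, with no new data. The drawback is a low-powered companion result that may leave the question open. Fixing both analyses in advance also prevents a choice between them after the results are seen.
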